6.2.2. Day 1 (Prior to injection)

A subject will be excluded from enrolment in this study if any of the following criteria apply on Day 1 (prior to injection):

Medical condition

31. Patients who have aspiration pneumonia, relapse of lower respiratory tract infection, uncontrollable asthma, uncontrollable COPD, and/or underlying or a history of serious respiratory dysfunction, which were clinically considered to be respiratory function impairment (e.g., SpO₂ <95%) by an investigator within 12 months before Day 1 visit
32. Patients who have a history of aspiration, or an underlying and/or a history of the symptoms that suggests high risks for aspiration by an investigator within 12 months before Day 1 (serious salivation requiring changing in a type of diet, chronic dysphagia that is difficult to swallow)

Preceding Treatments and Concomitant Medications/Therapies

33. Patients who were treated with botulinum toxin for spasticity of upper limb less than 16 weeks before Day 1 visit
34. Patients who underwent surgical interventions, phenol block, ethanol block or Muscle Afferent Block (MAB) within 12 months before Day 1 visit, or these interventions are planned during the study period in any one of the finger (upper limb), wrist, elbow or shoulder muscles, which will be involved in the study
35. Patients who placed a surgical cast or a dynamic splint within 3 months before Day 1 study visit, and/or these interventions are planned to be placed on the upper limb to be involved in the study

36. Patients who were injected corticosteroid or an anesthetic agent into the finger (upper limb), wrist, or shoulder flexors, which will be involved in the study within 3 months before Day 1 visit, or these injections are planned during the study
37. Patients who received CIMT (constraint-induced movement therapy) within 3 months before Day 1 visit or CIMT is planned during the blind phase
38. Patients who underwent ultrasound therapy, TENS (transcutaneous electrical nerve stimulation), electrical stimulation therapy, or acupuncture therapy in the upper arm, which will be involved in the study within 1 month before Day 1 visit, or these therapies are planned during the study

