Immunogenicity, drug resistance, antibody production	The important cause of neutralizing antibody production has not been fully clarified. A few studies suggested that the injection of the product at short intervals or at a high dose may lead to increased rate of antibody production[Jankovic, 2006; Klein, 2002]. Neutralizing antibody production against botulinum toxin type A may lead to inactivation of the biological activity of the product, resulting in decreased therapeutic effects of the product.	In this study, patients who were considered likely to have neutralizing antibody production based on the previous treatment experience of botulinum toxin type A will be excluded from enrolment in the study (Exclusion Criteria 6.2.1). In addition, treatment schedule in the study was set to ensure at least a 12-week dosing interval.
Other (If applicable)		
Medication error (preparation with lidocaine)	One fatal case due to anaphylaxis has been reported. In this case, the patient died after 100 units of an injection of the product that prepared inappropriately with 5 mL of 1% lidocaine. The causal relationship of death to the product and lidocaine, or both has been unknown.	In this study, the product will be prepared appropriately with 0.9% normal saline. The preparation method will be described on the study reference manual (SRM).

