6.2. Exclusion Criteria

6.2.1. Screening Phase (Day -28 to Day -1)

A subject will be excluded from enrolment in this study if any of the following criteria apply in the screening phase. Measurements of laboratory parameters at screening must be completed 7 days (± 3 days) before initial injection (Day 1).

Medical Condition

1. Patients present with spasticity requiring treatment in the non-paralytic side of the upper limb
2. Patients who have fixed contracture* in the finger (upper limb), wrist, elbow or shoulder muscle, which will be involved in the study
(*Positive effects were not confirmed in the previous treatment with GSK1358820, and contracture is considered to be the main cause of limited range of motion in the joint.)
3. Patients who have medically significant capsulitis or subluxation in any one of the fingers (upper limb), wrist, elbow and shoulder, which will be involved in the study, or whom an investigator considers the complicated local signs of pain may affect the efficacy evaluation
4. Patient's upper limb spasticity is attributed to other than stroke (traumatic brain injury, spinal cord injury, multiple sclerosis, or cerebral palsy)
5. Patients who have a 2-fold higher alanine aminotransferase (ALT) level than the upper limit of normal (ULN)
6. Patients who have a 1.5-fold higher bilirubin than the ULN (If a bilirubin fractionation shows direct bilirubin $< 35\%$, a 1.5-fold higher free bilirubin than the ULN is acceptable).
7. Patients whom the investigator considers presence of a current medical history of unstable liver diseases or biliary tract diseases (the condition will be defined by development of ascites, encephalopathy, coagulopathy, hypoalbuminemia, esophageal or gastric varices, persistent jaundice or hepatic cirrhosis)

Note:

- If a patient with stable chronic liver diseases (Gilbert's syndrome, silent gallstone, and stable chronic hepatitis B or hepatitis C [Namely, hepatitis B surface antigen: HBsAg or hepatitis C virus: HCV antibody shows positive at screening or within 3 months before initiation of the study treatment] are included) meets other inclusion criteria, the patient can be enrolled in the study.
8. Patients with QTc > 450 msec or QTc > 480 msec in patients with bundle branch block
Note:

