7.7.2. Contraindicated Medications/Therapies

Following drugs and therapies will be prohibited to use from screening phase through completion of the study:

- Botulinum toxin preparations
- Peripherally acting muscle relaxants
- (dantrolene sodium, suxamethonium chloride, pancuronium bromide, vecuronium bromide, rocuronium bromide)
- Antibiotic agents with neuromuscular junction blocking effects
 - Aminoglycosides (streptomycin sulfate, kanamycin sulfate, gentamicin sulfate, neomycin sulfate, spectinomycin hydrochloride, etc.)
 - Polypeptides (polymyxin B sulfate)
 - Lincomycins (lincomycin hydrochloride, clindamycin)
 - Enviomycin sulfate
- Nerve blocks such as phenol block, ethanol block and MAB for the upper limb
- Surgical cast or a dynamic splint
- A surgery for the upper limb
- A surgical cast or a dynamic splint for the upper limb
- Corticosteroid injection or an anesthetic agent for the upper limb
- Ultrasound therapy, TENS (transcutaneous electrical nerve stimulation), electrical stimulation therapy, or acupuncture therapy for the upper limb

Following drugs and therapies will be prohibited to use from screening phase through completion of the blinded-phase:

- CIMT (constraint-induced movement therapy)

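### Day 1 Exclusion 36 does not name the elbow, the primary-endpoint joint, and so disagrees with Exclusions 2, 3 and 34 and with the prohibition in 7.7.2

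*Protocol*

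**What the plan says.** All references are to the current (Amendment 2) text of the Protocol.

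- **Exclusion 36 (6.2.2)** applies to patients who were "injected corticosteroid or an anesthetic agent into the finger (upper limb), wrist, or shoulder flexors" within 3 months before Day 1, or in whom such injections are planned during the study. It names three sites.
- **Exclusion 34 (6.2.2)**, on surgery and on phenol, ethanol or muscle afferent blocks, applies "in any one of the finger (upper limb), wrist, elbow or shoulder muscles, which will be involved in the study". It names four sites, including the elbow.
- **Exclusion 2 (6.2.1)** reads "Patients who have fixed contracture* in the finger (upper limb), wrist, elbow or shoulder muscle". Exclusion 3 (6.2.1), on capsulitis, subluxation and local pain signs, also lists the elbow.
- **Section 7.7.2** prohibits, from screening to the end of the study, "Corticosteroid injection or an anesthetic agent for the upper limb". That wording takes in the elbow.
- **Section 8.2.5** requires withdrawal, with a completion visit first, when a prohibited therapy has to be started.
- **Section 10.3.1** defines the primary endpoint as a fall of at least one level in elbow MAS at Week 6 and counts a missing Week 6 score as non-response. Section 5.1 judges the result on whether the 400-unit point estimate exceeds the 240-unit one.

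**The concern.** The site missing from item 36 is the one on which the trial is judged. Elbow MAS is the primary endpoint, a Day 1 entry requirement (6.1.2, item 31) and the randomisation stratum (7.3). Two consequences follow from the text as written.

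First, the look-back. A patient given a corticosteroid or anaesthetic injection in the elbow flexors shortly before screening is not excluded by item 36, whereas the same injection in the wrist, finger or shoulder would exclude. The 7.7.2 prohibition does not close the gap, because it starts only at screening.

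Second, planned injections. A patient with an elbow injection planned during the study also passes item 36. Section 7.7.2 then forbids that injection and 8.2.5 removes the patient if it is needed. If this happens before Week 6, the likely result is a non-response that reflects an eligibility gap rather than the effect of treatment. The entry rule can thus admit someone whom the conduct rules would take out.

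**Working it through.** **Comparison of the text**

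| Provision | Period covered | Elbow covered? |
|---|---|---|
| Exclusion 2 (contracture) | at screening | yes, named |
| Exclusion 3 (capsulitis, subluxation, pain signs) | at screening | yes, named |
| Exclusion 34 (surgery, nerve blocks) | 12 months before Day 1, and planned | yes, named |
| Exclusion 36 (steroid or anaesthetic injection) | 3 months before Day 1, and planned | no |
| 7.7.2 (steroid or anaesthetic injection) | from screening to study end | yes, whole upper limb |

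The bracketed phrase after the word finger in item 36 cannot be read as bringing in the elbow. Exclusion 34 has the same bracket and still lists the elbow separately.

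**What remains uncovered**

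1. Before screening but within 3 months of Day 1: an elbow steroid or anaesthetic injection meets neither item 36 nor 7.7.2.
2. Planned for after screening: it passes item 36, is prohibited by 7.7.2 and leads to withdrawal under 8.2.5. The Schedule of Activities includes MAS at the withdrawal visit, so the subject would ordinarily have a post-baseline assessment and stay in the ITT population (10.2). Without a Week 6 score the subject is a non-responder (10.3.1).

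**Size, as an illustration only**

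The Protocol gives no share of affected patients, so none can be estimated. The plan's own figures come first. With 60 per group and responder rates of 70% and 50% (10.1), two-sided 5%:

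- Power is 61.1% with the pooled normal formula, 62.7% unpooled and 61.8% for the exact binomial power of the uncorrected chi-square test. The stated value of about 62% is reproduced.
- The probability that the 400-unit point estimate is the higher is 98.5% exactly. The unpooled normal formula gives 0.20 / √(0.70×0.30/60 + 0.50×0.50/60) = 2.28, or 98.9%. The stated value of at least 98% is reproduced.

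Now assume that a share f of each arm is affected and shows no difference between arms, with a common response rate r. The arm rates become 0.70(1−f) + rf and 0.50(1−f) + rf, so the difference is 0.20(1−f) whatever r is. For r from 30% to 70%:

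| f (assumed) | Difference | Power (pooled) | P(400 > 240), exact |
|---|---|---|---|
| 0 | 20 points | 61.1% | 98.5% |
| 5% | 19 points | 56–57% | about 98.0% |
| 10% | 18 points | 51–53% | 97.3–97.5% |
| 20% | 16 points | 42–44% | 95.4–95.8% |

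The complete absence of a treatment difference in affected patients is a deliberately unfavourable assumption. Power is shown only because the Protocol quotes it; no test is planned.

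**The case against.** The strongest reply is that other criteria already do most of the work. Elbow MAS must be at least 3 at both screening and Day 1, so a patient whose elbow tone is well reduced cannot enter. Exclusion 3 removes medically significant elbow capsulitis or subluxation, and local pain judged likely to affect the efficacy evaluation. Exclusion 34 removes elbow surgery and nerve blocks for 12 months. No passage states that a steroid or anaesthetic injection changes elbow MAS at Day 1 or Week 6. All of this stands, and it is why the point is small. It does not remove the conflict between item 36 and 7.7.2 with 8.2.5, which needs no clinical assumption. The change log for Amendment 1 (Appendix 8) gives consistency between 6.2.2 and 7.7.2 as the reason for adjusting both, so alignment was the sponsor's own aim.

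Three stronger readings are tempting and not supported.

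- **Toxin at other sites.** A reader might infer that Exclusion 33, which covers patients "treated with botulinum toxin for spasticity of upper limb less than 16 weeks before Day 1 visit", is also defective because toxin given outside the upper limb is not covered, against the statement in 3.3.1 that the "treatment schedule in the study was set to ensure at least a 12-week dosing interval". That statement concerns the spacing of study injections, and 7.7.2 bans toxin only from screening. A wider look-back would be a preference, not the repair of a contradiction.
- **Hidden exposure.** A reader might suppose that recent injections would go unrecorded. The Schedule of Activities collects medical history at screening and Day 1 and concomitant therapies from screening, and 7.7 requires medications in use at enrolment to be recorded.
- **Systematic bias.** Allocation is randomised and blinded in Part 1, so patients with a recent or planned elbow injection should fall in both arms alike. Nothing in the Protocol suggests that they would collect in one arm.

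**Conclusion.** Item 36 is inconsistent with Exclusions 2, 3 and 34 and with 7.7.2 and 8.2.5, and the inconsistency falls on the primary-endpoint joint. As written, it does not exclude a patient with an elbow steroid or anaesthetic injection shortly before screening. It also admits a patient with a planned elbow injection whom the conduct rules would then withdraw. This is a minor point that is worth correcting.

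The number affected is unknown and probably small. The expected effect is noise or dilution in the elbow responder rate, not bias between arms. Even if 5% of each arm were affected with no treatment difference at all, the chance of the 400-unit estimate being the higher would move only from 98.5% to about 98.0%. That calculation rests on the Protocol's assumed 70% and 50% rates and on an affected share that is purely assumed. The documents do not say whether leaving out the elbow was intended.

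**What to change.** Reconcile the site list in Exclusion 36 with Exclusions 2, 3 and 34, and with 7.7.2 and 8.2.5, for both the look-back and the planned-injection parts. If the difference is intended, say so and state how a planned elbow injection is to be handled at entry. The clinical rule and its interval are for the sponsor's clinicians to decide.

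From the medical history and concomitant therapy records, identify any enrolled subjects with a recent pre-screening elbow injection. If there are any, add a sensitivity analysis of the primary endpoint without them. Because that history precedes randomisation, leaving these subjects out does not select on a post-treatment event. Subjects withdrawn for an injection during the study should stay in the primary analysis under the existing non-responder rule.

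The cost is a short text amendment, possibly a few fewer eligible patients, and at most one extra table.

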6.3. Lifestyle Restrictions

No limitations are required.

6.4. Screen Failures

Screen failures are defined as participants who consent to participate in the clinical study but are not subsequently [randomized/entered in the study]. A minimal set of screen failure information is required to ensure transparent reporting of screen failure participants to meet the Consolidated Standards of Reporting Trials (CONSORT) publishing requirements and to respond to queries from regulatory authorities. Minimal information includes demography, screen failure details, and eligibility criteria.

Rescreening

If a patient does not meet the participation criteria in the study (dropout during screening), the patient may undergo second screening only 1 time. If a patient does not meet following items, contact the medical monitor of the sponsor and gain his/her consent because validity of rescreening in subjects who dropped out needs to be judged carefully in the light of medical aspects.

- Subjects who did not meet the inclusion criteria for MAS (Inclusion criteria 5 at screening) and dropped out (However, the dropout period will be for within only 1 month from the dropout).
- For some reasons, a subject cannot make a study visit or undergo examination
- Sample collection or examination cannot be performed because of procedural or technical problems

The investigator must carefully consider the ethical aspects of subjects, and if other treatments are considered to give more treatment benefits for a subject, rescreening must not be conducted.

The rescreened subjects will be allocated a different subject identification number as upon initial screening.

7. TREATMENTS

Study treatment product is defined as any investigational treatment(s), and placebo to administer to a study participant according to the protocol.

7.1. Treatments Administered

Study Treatment Name:	GSK1358820 (Nonproprietary name: Botulinum toxin type A)	Placebo
Dosage formulation:	Injection	Injection
Ingredient and quantity (Per vial)	Botulinum toxin A 100 units Sodium chloride 0.9 mg Human serum albumin 0.5 mg	Sodium chloride 0.9 mg
Packaging and Labeling	It will be listed on the labelling in accordance with the regulatory requirements in Japan.	It will be listed on the labelling in accordance with the regulatory requirements in Japan.
Manufacturer	Allergan (Ireland)	Allergan (Ireland)
Dose	400 units	240 units
Dosing instructions	
Part 1: 240 or 400 units of the product will be injected into the muscles that act on the finger (including thumb flexors), wrist and elbow flexors, in accordance with Table 2. In and after Part 2: 400 units of the product will be injected into the muscles that act on the finger (including thumb flexors), wrist, elbow and shoulder flexors in accordance with Table 3. For the muscles that the investigator considers unnecessary to be treated, an injection may be skipped. Dose intervals should be at least 12 weeks.
 
For adjustment of the product, the product will be dissolved with 2 ml of normal saline per 1 vial (100 units). The details will be described on Table 4.
	

In the blind phase

- A total of 240 units of product will be injected into the muscles that act on finger (including thumb flexors) and wrist flexors, and a total of 160 units of the product or placebo for the muscles that act on the elbow flexors in divided doses in accordance with [Table 2](#).
- The muscles which are not listed on [Table 2](#) must not be used.
- All of the muscles described on [Table 2](#) must be used. If the subject with no symptoms with thumb, the investigator does not have to inject to thumb.
- If the total dose for the muscles that act on the finger and wrists flexors is ensured by 240 units, and 160 units for the muscles that act on the elbow flexors, the dose can be adjusted at an investigator's discretion based on the symptoms of a subject.

In the open-label phase

- The investigator will decide the dose and the muscle to be injected based on the symptoms of patients, and a total of 400 units will be injected in divided doses. For the muscles that the investigator considers unnecessary to be treated, an injection may be skipped.
- The muscles to be injected must be chosen from [Table 3](#), and the muscles which are not listed on [Table 3](#) must not be used. For dose and number of injection site (sites/muscles), refer to [Table 3](#) and will be decided by investigator.

Table 2 Muscle Involvement and Dose in the Blind Phase

Number	Muscles	The 400 units group Dose (units)	The 240 units group Dose (units)	Number of injection site (site and muscles) ³	Joint
A1	Biceps brachii	70 ¹	Placebo	2	A.Elbow
A2	Brachialis	45 ¹		1	
A3	Brachioradialis	45 ¹		1	
B1	Flexor carpi radialis	50 ²	50 ²	1	B.Wrist
B2	Flexor carpi ulnaris	50 ²	50 ²	1	
C1	Flexor digitorum profundus	50 ²	50 ²	1	C.Finger
C2	Flexor digitorum superficialis	50 ²	50 ²	1	
D1	Flexor pollicis longus	20 ²	20 ²	1	D.Thumb
D2	Adductor pollicis	20 ²	20 ²	1	
	Total	400 ²	240 ²	1	-

1: Within the limits of the total of 160 units (the elbow flexors), the dose will be decided by an investigator depending on the patient's symptoms.

2: Within the limits of the total of 240 units (the finger and wrist flexors), the dose will be decided by an investigator depending on the patient's symptoms.

3: When the dose exceeds 50 U per muscle, take into account the divided-injection.

Table 3 Muscle Involvement and Reference Dose in the Open-Label Phase
(Modified partially of "Dosing, Administration, and a Treatment Algorithm for Use of Botulinum Toxin A for Adult-Onset Spasticity. [Brin, 1997]")

Number	Muscles ¹	Dose (units) ²	Number of injection site (Sites/muscles) ²	Joint
A1	Biceps brachii	50-200	4	A.Elbow
A2	Brachialis	25-75	2	
A3	Brachioradialis	25-75	2	
B1	Flexor carpi radialis	25-100	2	B.Wrist
B2	Flexor carpi ulnaris	10-50	2	
C1	Flexor digitorum profundus	25-100	2	C.Finger
C2	Flexor digitorum superficialis	25-75	4	
C3	Lumbricales interossei	10-50/hand	3	
D1	Flexor pollicis longus	5-25	1	D.Thumb
D2	Adductor pollicis	5-25	1	
D3	Opponens	5-25	1	
E1	Pronator teres	25-75	1	E.Forearms
E2	Pronator quadratus	10-50	1	
F1	Teres major	25-75	1	F.Shoulder
F2	Latissimus dorsi	50-150	4	
F3	Pectoralis major	75-150	4	
F4	Subscapularis	25-75	1	

(Brin MF and the Spasticity Study Group, 1997)

1: The muscles which are not listed on Table 3 must not be used

2: For dose and number of injection site (sites/muscles), refer to Table 3 and will be decided by investigator.

Table 4 Muscle Involvement and Reference Dose in the Open-Label Phase

Dose (units)	Injection Volume (ml)
100	2.0
95	1.9
90	1.8
85	1.7
80	1.6
75	1.5
70	1.4
65	1.3
60	1.2
55	1.1
50	1.0
45	0.9
40	0.8
35	0.7
30	0.6
25	0.5
20	0.4
15	0.3
10	0.2
5	0.1

7.2. Dose Modification

Not applicable

7.3. Method of Treatment Assignment

After completion of all evaluations at screening phase/initiation of the blind phase, the subjects who met the inclusion criteria and none of the exclusion criteria will be given their randomization number at a case registry center and randomized to either the 240 or 400 units group. The assigned randomization number cannot be re-used. The table of the allocation will be prepared via a computer in GSK, using the RandAll systems.

Based on the MAS score (3 or 4) in the elbow flexors, subjects will be stratified at the time of randomization.

The subjects who meet the eligibility for the injections in the open-label phase can move forward to the open-label phase and be injected (Refer to section 5.1.3). In the open-label phase, 400 units of the product will be given to all subjects. Other detailed information will be described on SRM.

7.4. Blinding

This study consists of the blind phase (Part 1), followed by the open-label phase (Part 2 and subsequent Parts), and in the blind phase, following processes are applied.

A Role of the Person Responsible for Investigational Product Assignment

The person who is responsible for investigational product assignment will prepare an operating procedure for the assignment. The operation will be conducted in accordance with the operating procedure. The person who is responsible for the investigational product assignment will display the drug number on a container of the investigational product (investigational product and control drug)

after checking of the investigational product (investigational product and control drug) and the indistinguishability of packaging appearance. The confirmation of the investigational product (investigational product and control drug) and the indistinguishability of packaging appearance will be also performed after completion of the study. In addition, an operating procedure for occasion where the emergency treatment disclosure is required will be prepared. In response to the request of disclosure, unblinding procedures are performed for the requested drug only.

The unblinded subjects by the investigator will discontinue participation in the study. In addition, the major reasons for discontinuation (the event(s) or condition led to unblinding) will be described on case report form (CRF).

The Global Clinical Safety and Pharmacovigilance (GCSP) of the sponsor may disclose the assigned treatment in the subject, who experienced serious adverse events. For serious adverse events requiring emergency report to the regulatory authority, a copy of an emergency report on the assigned treatment of the subject may be sent to the study involving investigator in accordance with the regulations, policy of the sponsor, or both.

